9.4 Secondary Efficacy Analysis

All secondary analyses will be performed on the ITT population. These analyses may be repeated on the mITT and PP populations.

9.4.1 $\geq 90\%$ Reduction in AF Burden

The AF burden, as a percentage, is recorded on the Holter Monitor eCRF. The recorded values and percent change from baseline in AF burden will be summarized by time point at 6, 12, and 18 months post-procedure.

The percent change from baseline at 12 months will be categorized as $\geq 90\%$ reduction (percent change $\leq -90\%$) or $< 90\%$ reduction (percent change $> -90\%$). The proportion of subjects achieving $\geq 90\%$ reduction at 12 months will be compared between treatment arms using Fisher's Exact test.

This analysis will be repeated for the following subsets of subjects:

- Subjects who have taken a Class I/III AAD during the efficacy evaluation period (excluding previously failed Class I/III AADs with no increase in dosage).

- Subjects who have *not* taken a Class I/III AAD during the efficacy evaluation period (excluding previously failed Class I/III AADs with no increase in dosage).
- Subjects who have taken any Class I/III AAD during the efficacy evaluation period.

No imputation will be performed for missing data.

These analysis (on all subjects and the three subsets) will also be repeated where subjects with a new or increased dosage of Class I/III AADs during the efficacy evaluation period will be categorized as not having achieved $\geq 90\%$ reduction. This will be performed on the ITT population. No imputation will be performed for missing data.

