##### **1.4.2 Secondary Objectives**

To demonstrate the efficacy of the procedure as a 90% reduction in the subject's baseline AF burden at 12 months post procedure in the presence or absence of class I / III AADs and a change in QOL measures and the six minute walk test scores from the baseline to 12 months post procedure.

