#### **6.1 Blanking Period**

The period from index procedure to the 3 month post procedure visit will be considered a blanking period. During the blanking period, the use of AADs, cardioversions, and any recurrence or episodes of AF will not be considered a treatment failure. Subjects who receive AF therapy (a new class I/III AAD, or an increase in dose of a previously failed class I/III AAD therapy, DCCV, pharmacological cardioversion, RFCA) following the 3 month blanking period through the 12 months post procedure follow-up visit will be considered primary efficacy failures. Subjects receiving RFCA for the treatment of AF, left-sided atypical atrial flutter, or atrial tachycardia at anytime (even within the blanking period) after the index procedure will be deemed primary efficacy failures; any RFCA should be performed in accordance with Attachment F – Repeat Catheter Ablation Protocol. Subjects in either arm of the study who are efficacy failures (documented by the 24 hour holter results), at the six month post procedure follow-up time point, may undergo an ablation procedure per physician recommendation. Subjects will be deemed efficacy failures, the ablation will be recorded as a rhythm disturbance treatment within the TEMPO EDC system, and the subjects will be continued to be monitored per protocol requirements.

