9.2 Multiplicity Adjustment

The fixed-sequence procedure[1,2] will be used to evaluate the following secondary endpoints. Each of these tests will be tested at the same significance level ($\alpha=0.05$) in this predetermined order. Each endpoint is only tested if the prior endpoint is successful ($p \leq 0.05$). This procedure does not inflate the Type I error rate since the sequence is prospectively specified and no further testing is performed once an endpoint in the sequence fails to show significance ($p > 0.05$)[2]. All tests will be performed on the ITT population. If sufficient data have not been collected during this study to permit the evaluation of a given endpoint, that endpoint should be skipped and the subsequent endpoint evaluated:

- 1) Achievement of $\geq 90\%$ reduction in baseline AF burden at 12 months post-procedure, where subjects with new or increased dosage of Class I/III AADs during the efficacy evaluation period are categorized as not achieving $\geq 90\%$ reduction, using the Fisher's Exact test as described in Section 9.4.1.

- 2) AF freedom during efficacy evaluation period, using the chi-square or Fisher's Exact test as described in Sections 9.4.5 and 9.1, where subjects with new or increased dosage of Class I/III AADs during the efficacy evaluation period are categorized as not achieving AF freedom.
- 3) Achievement of $\geq 90\%$ reduction in baseline AF burden at 12 months post-procedure, regardless of Class I/III AAD usage, using the Fisher's Exact test as described in Section 9.4.1.
- 4) AF freedom during efficacy evaluation period, using the chi-square or Fisher's Exact test as described in Sections 9.4.5 and 9.1, regardless of Class I/III AAD usage.
- 5) Change in AFSS composite score at 12 months post-procedure, using an ANCOVA model as described in Section 9.4.3.
- 6) Change in SF-36 physical health composite score at 12 months post-procedure, using an ANCOVA model as described in Section 9.4.2.
- 7) Change in SF-36 mental health composite score at 12 months post-procedure, using an ANCOVA model as described in Section 9.4.2.
- 8) Change in distance walked during six-minute walk test at 12 months post-procedure, using an ANCOVA model as described in Section 9.4.4.
- 9) Change in left ventricular ejection fraction (LVEF) at 6 months post-procedure, as described in Section 9.5.2.
- 10) Atrial remodeling assessed by a decrease in left atrial size at 6 months post-procedure, as described in Section 9.5.3.

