9.5 Exploratory Efficacy Analysis

9.5.1 Reduction from Baseline AF Burden at 18 Months

The reduction in AF burden from baseline to 18 months will be categorized and analyzed as described for the reduction in AF burden at 12 months (Section 9.4.1).

This analysis will be performed on the ITT population. No imputation will be performed for missing data.

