9.5.4 Hospitalizations

Hospitalizations will be recorded including start date, duration, and reason for hospitalization (cardiovascular, AF, other). All information will be listed by subject and date. The number of hospitalizations and total number of days hospitalized will be summarized by treatment arm as follows:

- Hospitalizations in the 12 months prior to study procedure (defined hospitalizations with start dates on or after the 365th day before the study procedure, and before the study procedure date).
- Hospitalizations for the 12 month period beginning on the day after the 6 month visit (see Section 7.4.2) through the 365th day after the 6 month visit.

The change in the number of hospitalizations between the two periods will be calculated for each subject as the number of hospitalizations in the 6-18 month period minus the number of hospitalizations in the 12 months prior to the study procedure. The change in the total number of days hospitalized will be calculated similarly. The change will not be calculated for subjects who withdraw from the study within 18 months after study procedure, and they will be excluded from analyses. No imputation will be performed.

The difference between treatment arms in the change in the number of hospitalizations will be analyzed using a Poisson model with treatment arm and the number of hospitalizations in the 12 months prior to the study procedure as covariates. The difference between treatment arms in the change in the total number of days hospitalized will be analyzed similarly. Both analyses will be performed on the ITT population.

9.5.5 **Rhythm Disturbance Treatments**

Rhythm disturbance treatments are defined as cardioversion (either electrical or pharmacological), AAD therapy, endocardial catheter ablation, or convergent procedure. The dates of treatments, as recorded on the Rhythm Disturbance Evaluation eCRF, will be used to determine the type and date of occurrence. The number of rhythm disturbance treatments will be summarized by treatment arm as follows:

- Rhythm disturbance treatments in the 12 months prior to study procedure (defined hospitalizations with start dates on or after the 365th day before the study procedure, and before the study procedure date).
- Rhythm disturbance treatments for the 12 month period beginning on the day after the 6 month visit (see Section 7.4.2) through the 365th day after the 6 month visit.

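### The SAP's AF-burden responder rules recode drug rescue but not repeat ablation, although Protocol 6.1 deems re-ablated subjects efficacy failures

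*SAP*

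**What the plan says.** **How burden response is defined.** SAP 9.4.1 states: "The AF burden, as a percentage, is recorded on the Holter Monitor eCRF". Response is a fall of at least 90% from baseline at 12 months. The section adds one version in which "subjects with a new or increased dosage of Class I/III AADs during the efficacy evaluation period will be categorized as not having achieved" that reduction. SAP 9.2 carries the same drug-only rule into test 1, "where subjects with new or increased dosage of Class I/III AADs during the efficacy evaluation period are categorized as not achieving" the threshold, and into tests 12 (at least 75% reduction), 13 (burden of no more than 12%) and 17 (90% reduction at 18 months). Test 3 is explicitly regardless of drug use and recodes nothing. SAP 9.5.1 says the 18-month reduction "will be categorized and analyzed as described for the reduction in AF burden at 12 months", and SAP 9.5.6 and 9.5.7 refer back to 9.4.1. None of these sections mentions repeat ablation.

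**What may happen to subjects in between.** Under Protocol 6.1, subjects in either arm who are failures on the 6-month Holter "may undergo an ablation procedure per physician recommendation". The same paragraph deems them efficacy failures and adds that "the subjects will be continued to be monitored per protocol requirements". Their later Holters are therefore collected, and SAP 5.1 analyses subjects as randomized.

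**What the endpoint is for.** Protocol 1.4.2 gives the aim: "To demonstrate the efficacy of the procedure as a 90% reduction in the subject's baseline AF burden at 12 months post procedure". SAP 2.1.3 describes it as the efficacy of EPi-Sense-AF.

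**The concern.** A Holter taken after a second ablation reflects the index procedure plus the rescue. Test 1 accepts this logic for drugs, since it turns a good Holter into a non-response when a new or increased Class I/III AAD was used. It does not do so for ablation, which is at least as direct a treatment of the index failure. Protocol 6.1 has a failure statement for exactly these subjects, and the SAP's burden rules do not carry it over.

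Test 1 stands first in the fixed sequence, and each later test is run only if the one before it succeeds. A result for test 1 that depends on how many subjects were re-ablated, and in which arm, can block or open the whole secondary family. The trial is open label and repeat ablation is at the physician's recommendation, so equal rates across arms cannot be taken for granted. The primary endpoint is not affected.

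**Working it through.** **1. One subject traced through the rules.** Suppose baseline burden is 100%, the 6-month Holter shows AF, ablation is repeated at month 7, no AAD is new or increased, and burden at month 12 is 0%.
- Percent change = (0 − 100)/100 × 100 = −100%, which is ≤ −90%. Tests 1 and 3: responder.
- Tests 12 and 13: −100% ≤ −75% and 0% ≤ 12%. Responder on both.
- Primary endpoint (Protocol 1.5.1): failure, because AF was documented after the blanking period and left-sided ablation was repeated.
- AF freedom (SAP 7.4.4, test 2): failure, because AF was found on the 6-month Holter.

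**2. The plan's own sample size, reproduced.** SAP 4 gives 40% vs 65%, two-sided α = 0.05, 80% power, 2:1 allocation and 10% dropout, for 102:51. With p̄ = (0.40 + 2 × 0.65)/3 = 0.567 and pooled variance, the control arm needs 46, so 46 + 92 = 138. Inflation gives 46 × 1.10 = 50.6, rounded up to 51, and 3 × 51 = 153. The figure reproduces. It is for the primary endpoint; the burden endpoints have no power figure of their own.

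**3. Illustration for test 1.** Assumptions, none of them in the documents:
- response without re-ablation equals the primary planning rates, 40% and 65%;
- a fraction r_C (control) or r_T (treatment) of index non-responders is re-ablated before the 12-month Holter;
- 60% of those then meet the 90% threshold.

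Observed rates become p_C = 0.40 + 0.60 × r_C × 0.6 and p_T = 0.65 + 0.35 × r_T × 0.6. Power is the exact probability that the two-sided Fisher test at 0.05 favours treatment, at 51 control and 102 treatment.

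| r_C | r_T | p_C | p_T | Difference | Power |
|---|---|---|---|---|---|
| 0 | 0 | 40.0% | 65.0% | 25.0 points | 80% |
| 30% | 30% | 50.8% | 71.3% | 20.5 points | 66% |
| 30% | 10% | 50.8% | 67.1% | 16.3 points | 44% |
| 10% | 30% | 43.6% | 71.3% | 27.7 points | 89% |

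For example, in the third row p_C = 0.40 + 0.60 × 0.30 × 0.6 = 0.508 and p_T = 0.65 + 0.35 × 0.10 × 0.6 = 0.671.

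**4. No difference between the index procedures.** Set both index rates to 50%. Without re-ablation, the chance of a significant result favouring treatment is 2.0%. With r_C = 10% and r_T = 30%, p_C = 0.50 + 0.50 × 0.10 × 0.6 = 53% and p_T = 0.50 + 0.50 × 0.30 × 0.6 = 59%, and the chance is 7.9%.

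**5. Sensitivity to sample size.** SAP 9.4.1 does not impute missing burden, so the evaluable sample may be nearer 46:92. The four powers are then 79%, 62%, 43% and 87%, and the two error figures are 2.3% and 9.2%. The pattern does not change.

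**The case against.** **The protocol already calls these subjects failures.** Protocol 6.1 says so without the word primary, although the paragraph uses that word elsewhere. This is the best contrary text. Its context is the primary endpoint, and no burden definition in the SAP refers to it, so a programmer following 9.4.1 would count the subject as a responder. What stands is that the two documents need reconciling; it would be wrong to say that no text bears on the matter.

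**As-observed burden is a legitimate target.** Protocol 1.5.2 defines burden response as a status at 12 months, and analysis is by randomized arm. For test 3, which ignores drug use by design, as-observed is defensible, and tests 12, 13 and 17 are exploratory. The argument is weaker for test 1, which already recodes one form of rescue. No strategy for repeat ablation is stated for any of them.

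**Dilution is not certain.** A reader might infer that the arm with more failures gets more rescue, so the difference must shrink. That holds with equal re-ablation rates among non-responders, but nothing in the documents ensures equal rates, and the last row of the table goes the other way.

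**Crossover is not established.** SAP 9.5.5 says: "Rhythm disturbance treatments are defined as cardioversion (either electrical or pharmacological), AAD therapy, endocardial catheter ablation, or convergent procedure". A reader might infer that control subjects may cross over. The list only names treatments to be counted, and it applies to the 12 months before the procedure as well. Protocol 6.1 directs repeat RF catheter ablation to Attachment F. The point does not need crossover.

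**The contrast with the freedom endpoints needs care.** SAP 7.4.4 and 7.4.5 intend repeat left-sided ablation to be a failure, but derive it from an ablation date equal to the 12-month visit date. Read literally, that misses an ablation at month 7. The traced subject fails AF freedom through the 6-month AF finding.

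**Conclusion.** The point holds as an unreconciled gap between Protocol 6.1 and the SAP's burden rules. Applied literally, SAP 9.4.1 and 9.2 can credit a re-ablated subject as a responder for the index procedure, in the first gate of the fixed sequence as well as in later tests. It is inconsistent for test 1 to recode drug rescue and leave ablation rescue alone.

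The size is unknown because the documents give neither re-ablation nor burden-response rates. Under the assumed rates, power for test 1 ranges from 44% to 89% around a no-re-ablation value of 80%, and the chance of a false claim for treatment can rise from 2.0% to 7.9%. These figures show sensitivity and are not forecasts. The documents do not support a claim that the bias runs in one direction, that control subjects are permitted to cross over, or that as-observed analysis is wrong for test 3. The change should be made, but it concerns secondary and exploratory endpoints only.

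**What to change.** Reconcile SAP 9.4.1 and 9.2 with Protocol 6.1, and carry the result into 9.5.1, 9.5.6 and 9.5.7.

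- **Tests 1, 12, 13 and 17:** add that a subject with any repeat left-sided ablation (catheter, surgical or convergent) after the index procedure, and on or before the date of the Holter used for that time point, is categorized as not achieving the burden threshold. At the least, do this for test 1.
- **Test 3:** state whether the same rule applies or whether the test is as observed.
- **Supportive table:** report the as-observed burden analysis alongside.
- **Cardioversion:** it is likewise not recoded in the burden rules, so state how it is handled.
- **SAP section 13:** record the change as a departure, because Protocol 1.5.2 does not name ablation for these endpoints.

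The cost is small. Ablation dates and locations are already on the Rhythm Disturbance Evaluation eCRF, and SAP 7.4.6 already provides for classifying the side without treatment arm shown, so no new data are needed. Responder percentages will fall slightly in both arms.

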9.4.2 SF-36

The SF-36^[4,5] is administered at the Baseline and 12 month visits. The SF-36 collects items across the physical functioning, role-physical, bodily pain, general health, vitality, social functioning, role-emotional, and mental health scales. Those scales are then combined into 2 overall summary measures, for physical health and mental health. Item scores are summed (after reverse coding the 10 items requiring it) to form the raw scale scores, which are rescaled to a 0-100 scale and standardized using a z-score transformation based on SF-36 scale means and standard deviations from the general U.S. population, as provided in the scoring manual^[2,3]. Aggregate scores for the physical and mental health components are then calculated using weighted averages of the standardized scale scores, and standardized into the physical and mental health component scores using a T-score transformation to have a mean of 50 and a standard deviation of 10. Lower scores reflect poorer quality of life.

The algorithm from scoring manual^[2,3] is provided as follows for ease of reference but [2,3] remains the definitive reference.

The raw scale scores are calculated as follows, where missing values (as long as <50% of item scores are missing) are imputed as the mean score of the other item scores, after any recoding of those scores has been performed:

- **Physical Functioning:** #3a, 3b, 3c, 3d, 3e, 3f, 3g, 3h, 3i, 3j – sum of scores, where ≥ 5 item scores are non-missing.
- **Role-Physical:** #4a, 4b, 4c, 4d – sum of scores, where ≥ 2 item scores are non-missing.
- **Bodily Pain:** #7, 8 – sum of scores, where at least 1 item score is non-missing:
 - #7 recoded, 1 \rightarrow 6.0, 2 \rightarrow 5.4, 3 \rightarrow 4.2, 4 \rightarrow 3.1, 5 \rightarrow 2.2, 6 \rightarrow 1.0
 - #8 recoded, based on item score and original (pre-coded) score for

item #7: if score for #7 and #8 are both 1, recode #8 to 6; if score for #7 is 2 – 6 and score for #8 is 1, recode #8 to 5; if score for #8 is 2 – 5 and item #7 is non-missing, recode #8 to (6-score). If item #7 is missing, recode #8 to: 1 → 6.0, 2 → 4.75, 3 → 3.5, 4 → 2.25, 5 → 1.0.

- **General Health:** #1, 11a, 11b, 11c, 11d – sum of scores, where ≥ 3 item scores are non-missing.
 - #1 recoded, 1 → 5.0, 2 → 4.4, 3 → 3.4, 4 → 2.0, 5 → 1.0.
 - #11a and #11c: not recoded.
 - #11b and #11d: recoded as 6 – score.
- **Vitality:** #9a, 9e, 9g, 9i – sum of scores, where ≥ 2 item scores are non-missing.
 - #9a and #9e: recoded as 7 – score.
 - #9g and #9i: not recoded.
- **Social Functioning:** #6, 10 – sum of scores, where at least 1 item is non-missing and #6 is reverse coded using 6 – score and #10 is not recoded.
- **Role-Emotional:** #5a, 5b, 5c – sum of scores, where ≥ 2 item scores are non-missing.
- **Mental Health:** #9b, 9c, 9d, 9f, 9h – sum of scores, where ≥ 3 item scores are non-missing.
 - #9b, #9c and #9f: not recoded.
 - #9d and #9h: recoded as 7 – score.

The scores are then recalibrated into transformed scale scores using the formula $100 * ((\text{actual raw score} - \text{lowest possible raw score}) / \text{possible raw score range})$, to rescale them to a 0-100 scale. Specifically, the transformed scores are calculated as:

- Physical Functioning (PF): $100 * ((\text{actual raw scale score} - 10) / 10)$
- Role-Physical (RP): $100 * ((\text{actual raw scale score} - 4) / 4)$
- Bodily Pain (BP): $100 * ((\text{actual raw scale score} - 2) / 10)$
- General Health (GH): $100 * ((\text{actual raw scale score} - 5) / 20)$
- Vitality (VT): $100 * ((\text{actual raw scale score} - 4) / 20)$
- Social Functioning (SF): $100 * ((\text{actual raw scale score} - 2) / 8)$
- Role-Emotional (RE): $100 * ((\text{actual raw scale score} - 3) / 3)$
- Mental Health (MH): $100 * ((\text{actual raw scale score} - 5) / 25)$

Each of the raw scale scores is then adjusted by the specific mean and standard deviation for that scale to create a standardized scale score:

- $\text{PF_Z} = (\text{PF} - 84.52404) / 22.89490$

- $RP_Z = (RP - 81.19907) / 33.79729$
- $BP_Z = (BP - 75.49196) / 23.55879$
- $GH_Z = (GH - 72.21316) / 20.16964$
- $VT_Z = (VT - 61.05453) / 20.86942$
- $SF_Z = (SF - 83.59753) / 22.37642$
- $RE_Z = (RE - 81.29467) / 33.02717$
- $MH_Z = (MH - 74.84212) / 18.01189$

The physical and mental health component scores are created from the standardized scale scores, weighted by specific factor score coefficients. If any of the scale scores are missing, the component score will also be missing:

- Physical health component aggregate score (AGG_PHYS) = $0.42402*PF_Z + 0.35119*RP_Z + 0.31754*BP_Z + 0.24954*GH_Z + 0.02877*VT_Z - 0.0073*SF_Z - 0.19206*RE_Z - 0.22069*MH_Z$
- Mental health component aggregate score (AGG_MENT) = $-0.22999*PF_Z - 0.12329*RP_Z - 0.09731*BP_Z - 0.01571*GH_Z + 0.23534*VT_Z + 0.26876*SF_Z + 0.43407*RE_Z + 0.48581*MH_Z$

The scores are then transformed to the norm-based (50, 10) scoring as follows:

- Physical health component score (PCS) = $50 + AGG_PHYS*10$
- Mental health component score (MCS) = $50 + AGG_MENT*10$

The transformed scale scores (on a 0-100 scale) and norm-based component scores, and their changes from baseline, will be summarized by time point and treatment arm. Raw item scores, as well as transformed scale scores and norm-based component scores will be listed by subject.

The changes from baseline at 12 months will be analyzed using an analysis of covariance (ANCOVA) model with the scale or component score as the dependent variable, and treatment arm and baseline scale or component score as covariates.

9.4.3 Atrial Fibrillation Severity Scale (AFSS)

The University of Toronto's AF Severity Scale is also administered at the Baseline and 12 month visits. An overall subject-perceived severity score will be created by taking the mean of the results from item #7 (severity of most recent episode of irregular heart rhythm) and item #8 (severity of first episode of irregular heart rhythm), both scored as 1 = not at all severe and 10 = extremely severe. A composite score for total AF burden will be calculated by adding overall severity score to the result from item #5 (average frequency of AF, scored from 1=continuous to 11=less than once a year) and the result from item #6 (average duration of AF, scored from 1=continuous to 8=a few minutes), resulting in a range of possible scores from 3 – 29.

This calculation was described previously^[6] although Dorian et al erroneously stated the possible score range as 3-30. If any of the item results making up either the subject-perceived severity score or the composite score is missing, that score will also be missing.

Individual item results, as well as the composite score, will be listed by subject and time point. The results for items #4 (global well-being, scored 1-10), #5 (AF frequency), and #6 (AF duration), as well as the overall severity score and composite score will be summarized by time point and treatment arm, as will their change from baseline.

The changes from baseline at 12 months will be analyzed separately for each of those five scores using an ANCOVA model with the score as the dependent variable, and treatment arm and baseline score as covariates.

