2.3.2 Secondary Efficacy Endpoints

The secondary efficacy endpoints are:

- Success or failure to achieve a 90% reduction from baseline AF burden and off all Class I and III AADs at 12 months post-procedure.
- Success or failure to achieve a 90% reduction from baseline AF burden regardless of their Class I and III AAD status at 12 months post-procedure.
- Change in SF36 Quality of Life (QoL) scale scores and composite scores from baseline values to 12 months post-procedure.
- Change in University of Toronto Atrial Fibrillation Symptom Scale (AFSS) composite score from baseline values to 12 months post-procedure.
- Change in distance walked during the 6 minute walk test from baseline values to 12 months post-procedure.
- Success or failure to be AF free and off all Class I and III AADs except for a previously failed or intolerant Class I or III AAD with no increase in dosage following the 3 month blanking period through the 12 months post-procedure follow-up visit.
- Success or failure to be AF free, regardless of Class I and III AAD status following the 3 month blanking period through the 12 months post-procedure follow-up visit.

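### The AFSS composite in SAP 9.4.3 adds a higher-is-worse severity score to two higher-is-better items without recoding, so the worst possible state scores 12 and the best scores 20

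*SAP*

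**What the plan says.** SAP 9.4.3 first averages items #7 and #8 into a severity score, "both scored as 1 = not at all severe and 10 = extremely severe". It then gives the combination rule: "A composite score for total AF burden will be calculated by adding overall severity score to the result from item #5" and to item #6. The results added are those of "item #5 (average frequency of AF, scored from 1=continuous to 11=less than once a year) and the result from item #6", the latter being "average duration of AF, scored from 1=continuous to 8=a few minutes". The section gives a possible range of 3 to 29, says "This calculation was described previously", and cites a published source whose stated range it corrects from 3–30. It does not mention recoding items #5 and #6, and it does not say whether a higher or a lower composite is better. The other places that use the composite (SAP 2.3.2, 9.2 and 9.3.4, and the table list in 15.1.1) do not say either.

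The SF-36 section just before it, SAP 9.4.2, does both. On recoding it says "Item scores are summed (after reverse coding the 10 items requiring it) to form the raw scale scores", followed by item-level rules. On direction it says "Lower scores reflect poorer quality of life".

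The composite is a listed secondary endpoint in SAP 2.3.2: "Change in University of Toronto Atrial Fibrillation Symptom Scale (AFSS) composite score from baseline values to 12 months post-procedure". In SAP 9.2 it is test 5 of a 19-step fixed sequence. Each step is passed at p ≤ 0.05, two-sided by the default in SAP 6.5.

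**The concern.** A sum measures burden only if all its parts point the same way. Here one part falls as the patient improves and the other two rise. This is more than a sign convention. If all three parts pointed the same wrong way, the p-value would not change and a note on direction would be enough. Because they oppose each other, real improvements cancel within the score, and no statement of direction can restore what has cancelled.

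Two things could go wrong at test 5. A true difference between arms could be diluted until the test fails, which stops the sequence before tests 6 to 19. Or the test could pass on a difference whose sign is read backwards, since passing depends only on the p-value. The baseline composite is also a candidate covariate for the multiple imputation model in SAP 9.3.4.

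**Working it through.** **Inputs, all from SAP 9.4.3**

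| Part | Range | Higher means |
|---|---|---|
| Severity S = (item #7 + item #8)/2 | 1 to 10 | worse |
| Item #5, frequency | 1 to 11 | less frequent, better |
| Item #6, duration | 1 to 8 | shorter, better |

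As written: C = S + #5 + #6. Reversed: R = S + (12 − #5) + (9 − #6).

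**The plan's own range.** Minimum 1+1+1 = 3 and maximum 10+11+8 = 29, so the stated 3 to 29 is reproduced. R has the same limits, so the range cannot show which coding was meant.

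**Extremes**

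| State | As written | Reversed |
|---|---|---|
| Worst: S = 10, #5 = 1, #6 = 1 | 10+1+1 = 12 | 10+11+8 = 29 |
| Best: S = 1, #5 = 11, #6 = 8 | 1+11+8 = 20 | 1+1+1 = 3 |

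As written, the end points are mixed states: 3 is continuous AF of the lowest severity, and 29 is the rarest and briefest AF of the highest severity.

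**Two example subjects.** Item #8 (first episode) is held at 8, on the assumption that the rating of a past event does not change.

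- Subject A goes from continuous AF with item #7 = 8 to the best category on items #5 and #6 with item #7 = 2. As written: (8+8)/2+1+1 = 10 becomes (2+8)/2+11+8 = 24, a rise of 14. Reversed: 8+11+8 = 27 becomes 5+1+1 = 7.
- Subject B moves item #5 from 4 to 5, item #6 from 3 to 4 and item #7 from 8 to 4. All three improve. As written: 8+4+3 = 15 becomes 6+5+4 = 15, no change. Reversed: 8+8+6 = 22 becomes 6+7+5 = 18.

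**How often the sign goes which way.** Count every combination in which item #5, item #6 and severity all improve, with equal weights. Improving pairs number 55 for item #5, 28 for item #6 and 45 for a 1–10 score, so 55 × 28 × 45 = 69,300 combinations for each of the first two rows. The third row counts every pair of item #7 and #8 ratings whose mean falls.

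| How severity moves | C rises | C falls | No change |
|---|---|---|---|
| Mean severity in whole points | 77.3% | 15.3% | 7.3% |
| Item #8 fixed, item #7 falls | 95.4% | 2.8% | 1.8% |
| Items #7 and #8 both free, half points allowed | 90.0% | 7.3% | 2.6% |

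With item #8 fixed, the mean improvements are 4.00 (item #5), 3.00 (item #6) and 1.83 (severity). Mean change as written: 4.00 + 3.00 − 1.83 = +5.17. Reversed: −(4.00 + 3.00 + 1.83) = −8.83. The signs are opposite, and the size is smaller by 1 − 5.17/8.83 = 0.41.

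These counts illustrate the scoring rule. They do not forecast trial data.

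**Between arms.** Let d5, d6 and dS be the between-arm differences in mean improvement on the three parts. The difference in mean change is d5 + d6 − dS as written and −(d5 + d6 + dS) reversed. If treatment helps on all three, the first is always the smaller in size, and it is zero when dS = d5 + d6. The effect on power also depends on standard deviations and correlations, which the documents do not give.

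**The case against.** - **The source may recode.** The SAP cites a published calculation, and its authors read it closely enough to correct the range. If the source reverses items #5 and #6, this is an incomplete transcription. If it sums them raw, the SAP follows the published score, and changing it would change the instrument's scoring. This stands: what is certain is the text, not the score that will finally be programmed. But 9.4.3 writes out a complete rule, and a programmer following it would not recode. SAP 9.4.2 names its manual as the definitive reference and still prints the recoding; 9.4.3 does neither.
- **The stake is smaller than 14 tests suggests.** Of tests 6 to 19, only 6 to 8 (the two SF-36 components and walk distance) are secondary endpoints. Tests 9 to 19 are exploratory under SAP 2.3.5, and several depend on data being available. This also stands. The count of 14 is right, but most of the tests behind test 5 carry less weight.
- **The enumeration is not a power calculation.** It has no arms, variances or correlations, and its whole-point version does not match a mean of two integer items. Agreed on both counts. The half-point version gives 90.0%, 7.3% and 2.6%, which leaves the conclusion unchanged, and the 41% is a reduction in mean change within one set, not a loss of power.
- **A wrong sign would be noticed.** Severity, item #5 and item #6 are each analysed separately, so a composite moving against its label would be visible. This protects the interpretation. It does not protect test 5, because only the composite is in the sequence.
- **Direction is also unstated elsewhere,** for example for walk distance (9.4.4) and LVEF (9.5.2). True, but those are single measures in which nothing cancels.

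**Conclusion.** The concern holds for the rule as written. SAP 9.4.3 defines a score that does not order patients by AF burden: worst 12, best 20, against 29 and 3 with items #5 and #6 reversed. When all parts improve, the score usually rises, sometimes falls or stays put, and always changes by less than a consistently coded score would. The conclusion rests on the item anchors printed in the SAP and on the absence of any recoding instruction there; the cited source could not be consulted.

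The reach is limited. The primary efficacy and safety analyses are untouched, test 5 is reached only if tests 1 to 4 succeed, and the components are reported separately. The effect on the power of test 5 is not quantified. This should be fixed before the data are analysed, because it affects the result of a named secondary endpoint and whether the three secondary endpoints after it can be tested.

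**What to change.** Check how the cited source scores items #5 and #6. Subject to that check, write into SAP 9.4.3:

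- composite = severity + (12 − item #5) + (9 − item #6);
- range 3 to 29, where higher means more burden;
- a negative change from baseline favours treatment.

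If the source does sum the raw items, the SAP should say so and justify keeping a score whose parts oppose each other as test 5. For the separate analyses of items #5 and #6, stating the direction of benefit is enough.

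The cost is one look at the source, one sentence in the SAP and one line in the derivation program. The individual items are already collected, so no new data are needed.
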